##### *c. Sample size determination and power analyses*

We target a 95% confidence level for our study. For a confidence interval of 15%, the sample size is 32. A 15% confidence level is sufficient for a feasibility study.

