- Following baseline and prior to the intervention phase, participating staff will take part in group training, with extra support as needed.
- During the intervention phase, a period of six weeks, the same dyads (or as close to same as is practical) will be assigned a schedule incorporating DWS followed by the same ADL routine as baseline.
- Each resident-participant will have two DWS per week. Staff-participants will spread this load across their shifts, averaging eight DWS sessions per 5-day week. We anticipate that session durations will average five minutes with variability according to resident-participants' individual interest levels on a given day. Staff schedule during study:

Mon 1h 10m	Tue 55m	Wed 1h 10m	Thu 55m	Fri 1h 10m
Res A DWS	Res A Mouth Care	Res A DWS	Res A Mouth Care	Res A Mouth Care
	Res B Mouth Care		Res B DWS	Res B Mouth Care
Res A Mouth Care	Res C DWS	Res A Mouth Care		Res C DWS
Res B DWS		Res B Mouth Care	Res B Mouth Care	
Res C Mouth Care	Res C Mouth Care	Res C Mouth Care	Res C Mouth Care	
Res B Mouth Care	Res D Mouth Care	Res D DWS	Res D Mouth Care	Res D DWS
Res C Mouth Care				
Res D Mouth Care		Res D Mouth Care		Res D Mouth Care
Reporting				

- Procedure for running a DWS

- **Initiating a session:**

Prior to the ADL, the dyad will sit in a quiet nook or the resident's bedroom with appropriate lighting. The care staff will ask the resident if they are comfortable (e.g. need a drink, need to go to the toilet, is comfortably dressed, has glasses and hearing aids in place).

To initiate the session, the care staff will open DevaWorld on the tablet device and invite resident to join.

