Reliability  
A staff champion (internal) will be appointed to oversee adherence to the study and liaise with the research team about any obstacles they notice along the way, such as

absenteeism or the need for extra training. A research assistant (external), in the role of reliability observer, will be assigned to track data, checking for reporting compliance and anomalies. The PI will review data week-by-week to ensure the study design continues to fit its purpose.

- Data collected at Baseline

Residents

- **Demographic variables:** Gender, age, race, ethnicity, marital status, socioeconomic status, languages spoken/language preference.
- **Stage of dementia** The Global Deterioration Scale for Assessment of Primary Degenerative Dementia (GDS) (16)
- **Cognitive Function:** The Mini Mental State Exam (MMSE) (20).
- **Functional stage** (Functional Assessment Staging Tool (FAST), (22): The FAST is used to describe the stages of dementia and employs a seven-stage system based on one's level of functioning and ability to perform daily living activities.
- **Time since admission** to facility (in months) {subtract date of admission from date of assessment).
- **Quality of life:**  
-DEMQOL/DEMQOL-proxy (23).
- **Response Behaviors**  
- The Neuropsychiatric Inventory (NPI): Assessing psychopathology in dementia patients. (24).
- **ADL capacity**  
Alzheimer's Disease Cooperative Study Activities of Daily Living Inventory (ADCS-ADL) 19- item inventory to assess activities of daily living for clinical trials in Alzheimer's disease. (25).

Care Staff

- **Demographics:** Age, gender, race, ethnicity, number of years of schooling and highest degree obtained, US or foreign born; languages spoken/language preference, marital status, currently or previously the primary informal caregiver of a person with dementia (a predictor of job satisfaction (26). Job background: Years as a CNA, years working for this employer, employed full or part time.
- **Burnout:** Copenhagen Burnout Inventory (27).
- **Sense of Competence:** Sense of Competence in Dementia Care Staff (SCIDS) (28).
- **Attitudes towards People with Dementia:** Approaches to Dementia Questionnaire (ADQ) (29).
- **Job Satisfaction:** Minnesota Satisfaction Questionnaire, Short-form (30).

Baseline data for Usual ADLs – No Intervention

- Staff's usual reporting at the end of each shift.
- Additional: the survey webpage.
  - Subject name
  - Time: start of ADL and stop ADL

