## IX. Analysis Plan

*Describe statistical analysis methods as appropriate. For example, will intention-to-treat methodology be used in the analysis? Will there be any sample stratification?*

- Thematic and sentiment analysis of tablet-recorded spoken and visual exchanges during DWS and post-session comments
- Statistical and text analyses of questionnaire responses
  - Statistical Analysis Plan
    - Assessment inventories with scores on the inventory's scale
    - Measuring mean value and standard deviation for the group
    - Complete a superiority statistical test
    - P-values calculated by t-test, 1 sided

HIPAA-compliant data capture software; eg REDCap, will be used to create the database and analyses. <https://www.project-redcap.org/>

Data will be reported graphically or with summary measure (e.g., means and standard errors or median and 95% confidence intervals), and subjected to statistical analysis when appropriate. Completion rates and grades scores will be presented as proportions and percentages.

ADCS-ADL scores will be compared from end of baseline to biweekly scores to the end of intervention and may be analyzed using a paired Student's t-test or the Wilcoxon signed-rank test if the data are not normally distributed.

Completion rates will be the percentage of all dyads who complete the entire eight weeks of study. The ratio of positively graded scores per dyad will be calculated to obtain the level of satisfaction of dyads and indicate the acceptability of DWS.

Aim 1: Successful primary outcomes are >55% completion rate and a statistically significant difference between assessments of completers and non-completers, indicating tolerability and acceptability of routine DWS.

Aim 2: The secondary outcome is to determine the feasibility of DevaWorld as an assistive tool for preparing and completing ADLs. Improved dyad outcomes are less time to complete ADLs, a reduction in negative response behaviors associated with the ADL, greater interest in the ADL, Care staff indicates tasks are easier than before.

Outcomes measures for baseline and intervention will be the same. As the score sheets cover a broader range of ADLs than those depicted in DW, overall and individual ADL scores will be analyzed and subjected to statistical tests. Our null hypothesis will be no statistical differences between ADL scores during the intervention and baseline phases

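### The ADCS-ADL total and its individual items are all tested against one general null, with no deciding comparison and no multiplicity control, so an isolated significant item would be weak evidence.

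*Combined protocol and SAP*

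**What the plan says.** Section IX (Analysis Plan) commits to inferential testing of the ADL score sheets at two levels: "overall and individual ADL scores will be analyzed and subjected to statistical tests". The reason given is that the sheets cover more activities than DevaWorld depicts, but no subset of items is named. The hypothesis is a single general one: "Our null hypothesis will be no statistical differences between ADL scores during the intervention and baseline phases". The same section calls for a superiority test and states "P-values calculated by t-test, 1 sided".

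On the instrument, the baseline measures in section VI.c.ii describe the ADCS-ADL as a "19- item inventory to assess activities of daily living for clinical trials".

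On timing, section IX says "ADCS-ADL scores will be compared from end of baseline to biweekly scores to the end of intervention". The procedures in section VI.c.ii list the sheet only twice: once when the baseline period ends, and once under the end-of-study assessments.

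On the error rate, the nearest statement is in section V.c: "We target a 95% confidence level for our study". The documents give no per-test alpha, testing order, multiplicity adjustment, key ADL score or key time point. The item tests are not labelled exploratory.

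**The concern.** The null refers to ADL scores in general, and the plan does not say which comparison decides it. A report could therefore present any one significant item, or the total, as rejecting the null. The chance that something crosses the threshold when DevaWorld has no effect is then the error rate of the whole family, which is well above that of a single test.

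The item set makes this worse. By the plan's own account, the sheet includes activities that DevaWorld does not depict. A chance gain on one of those would count just as much as a gain on a targeted activity.

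At stake is the ADL-score evidence for Aim 2. Section III makes support for real-world ADLs the primary objective, and section II intends the evidence to help build a regulatory case. A reader of the results needs to know whether a positive item was the planned test or one of twenty.

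**Working it through.** The plan states no familywise error rate, so there is no figure of its own to reproduce on this point. The only related arithmetic is the sample size: 32 / (1 − 0.20) = 40, which agrees with section VI.a.

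**Inputs**
- Tests per time point: 19 items + 1 total = 20 (sections VI.c.ii and IX). Nineteen is the only item count in the documents.
- Time points: one post-baseline under section VI.c.ii. Under section IX, biweekly over "During the intervention phase, a period of six weeks" gives 6 / 2 = 3, so up to 20 × 3 = 60 tests.
- Per-test alpha: not stated. Assumed 0.05, from the 95% confidence level; 0.025 one-sided is the stricter reading.
- Evaluable residents: 32 (section V.c).
- Correlation between items, and between time points: not in the documents, so a range is shown.

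**Independent tests.** P(at least one false positive) = 1 − (1 − α)^k.
- k = 20, α = 0.05: 1 − 0.95^20 = 64.2%
- k = 20, α = 0.025: 1 − 0.975^20 = 39.7%
- k = 60, α = 0.05: 1 − 0.95^60 = 95.4%
- k = 60, α = 0.025: 1 − 0.975^60 = 78.1%

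**Correlated tests.** One-sided paired t-tests were simulated with no true change: n = 32, 19 equally correlated items plus their sum, 8,000 replicates. In the three-time-point column, the range covers between-time correlations of 0.7 to 0.5.

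| Item correlation | One time point, α = 0.05 | One time point, α = 0.025 | Three time points, α = 0.05 |
|---|---|---|---|
| 0 | 63% | 39% | 88–91% |
| 0.1 | 55% | 35% | 80–85% |
| 0.2 | 49% | 31% | 74–79% |
| 0.3 | 44% | 27% | 67–72% |
| 0.5 | 33% | 21% | 54–60% |
| 0.7 | 24% | 15% | 41–46% |

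A repeat of the one-time-point columns with 40,000 replicates agreed to within 1.5 percentage points (23.9% and 14.4% in the last row). The first row is slightly below the formula because the total is the sum of the items and so is not independent of them.

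**With control.** One named test has an error rate of α. Bonferroni over 20 tests uses 0.05 / 20 = 0.0025 each, and 1 − 0.9975^20 = 4.9%.

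**The case against.** The strongest case on the other side has four parts.

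1. **The size depends on assumptions.** A reader might infer that a spurious ADL improvement is more likely than not. The documents do not support that as a flat statement. It needs 0.05 per test, which is not stated, and either nearly independent items or testing at all three biweekly points. Items of one scale rated by the same staff member are plausibly correlated. With one post-baseline assessment the rate drops below one half from an item correlation of about 0.2, and at 0.025 it is below one half even under independence. This part stands.

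2. **The 60-test case may not exist.** A reader might take 95%, or 60 × 0.05 = 3 expected false positives, as the plan's error burden. Those figures rest on biweekly sheets that the procedures do not schedule, and the 95% also needs full independence. This stands too: they are an upper bound, conditional on how the two sections are reconciled.

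3. **Aim 2 has other outcomes.** A reader might infer that Aim 2 rests on these tests alone. Sections V.d and IX list success through care challenges, time on ADLs, negative response behaviors, interest in the ADL, and staff attitudes or ease of tasks. Neither list names ADCS-ADL items, and no text makes one significant item sufficient for Aim 2. The concern is limited to the ADL-score part.

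4. **This is a single-arm feasibility study and Aim 2 is secondary.** Unadjusted secondary tests are common in such studies. That would be a sufficient answer if the plan called the tests exploratory. Instead it uses a superiority test, one-sided p-values and a stated null, and section III gives ADL support as the primary objective. This part lowers the priority but does not remove the point.

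**Conclusion.** The concern holds in a limited form. Section IX tests the total and the individual items against one null with nothing to say which result decides. In every scenario examined, the chance of at least one false-positive improvement is well above 5%. With one post-baseline time point and 0.05 per test, it is 64% under independence and roughly 24% to 55% for item correlations of 0.7 to 0.1. At 0.025 one-sided it is about 14% to 40%. It is higher if biweekly scores are also tested.

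These sizes assume the 19-item version, every item tested, an alpha that the plan does not state, and equal correlation between items. They do not show that a false positive is more likely than not. What they do show is that an isolated significant item would be weak support for the ADL-score part of Aim 2. The plan should be changed before analysis.

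**What to change.** Before analysis, amend section IX to:

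1. Name the comparison that decides the ADL-score null, end of baseline versus end of intervention, and state its alpha and sidedness. Use either the ADCS-ADL total, or a pre-listed set of DevaWorld-depicted items with Holm adjustment. As an illustration of the second option, four items at 0.05 unadjusted would give 1 − 0.95^4 = 18.5% under independence; Holm would test the smallest p-value at 0.05 / 4 = 0.0125 and hold the family at 5%.
2. Report all other items and any intermediate time points as estimates with 95% confidence intervals, labelled exploratory and with no significance claim.
3. Reconcile section IX with the assessment schedule in section VI.c.ii, so that it is clear whether biweekly ADCS-ADL scores are collected.

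The cost is wording only: no extra residents, visits or data. There are two downsides. An isolated item result can no longer be presented as confirmatory. If the total is chosen, activities that DevaWorld does not target may dilute an effect; the pre-listed item set avoids that, at the price of a stricter threshold per item.

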## **X. Timing**

From the start of baseline to when the study ends will be about 2 months.

